11. Patient has clinically significant, uncontrolled heart disease and/or recent cardiac event (within 6 months), such as:
 - Unstable angina within 6 months prior to screening.
 - Myocardial infarction within 6 months prior to screening.
 - History of documented congestive heart failure (New York Heart Association functional classification III-IV).
 - Uncontrolled hypertension defined by a Systolic Blood Pressure (SBP) \geq 160 mm Hg and/or Diastolic Blood Pressure (DBP) \geq 100 mm Hg, with or without anti-hypertensive medication. Initiation or adjustment of antihypertensive medication (s) is allowed prior to screening.
 - Ventricular arrhythmias.
 - Supraventricular and nodal arrhythmias not controlled with medication.
 - Other cardiac arrhythmia not controlled with medication.
 - Corrected QT (QTcF) $>$ 470 msec using Fridericia's correction on the screening ECG (as mean of triplicate ECGs).
12. Patient receiving treatment with medications that meet one of the following criteria and that cannot be discontinued at least 1 week prior to the start of treatment with LDK378 and for the duration of the study ([Appendix 1](#)):
 - Strong inhibitors or strong inducers of CYP3A4/5.
 - Medications with a low therapeutic index that are primarily metabolized by CYP3A4/5 and/or CYP2C9.

- Medications with a known risk of prolonging the QT interval or inducing Torsades de Pointes.

13. Patient has impairment of GI function or GI disease that may significantly alter the absorption of LDK378 (e.g., ulcerative diseases, uncontrolled nausea, vomiting, diarrhea, or malabsorption syndrome).

14. Patient is currently receiving treatment with warfarin sodium (Coumadin®) or any other coumarin-derivative anticoagulants.

15. Patient is receiving unstable or increasing doses of corticosteroids. If patients are on corticosteroids for endocrine deficiencies or tumor-associated symptoms (non-CNS), dose must have been stabilized (or decreasing) for at least 5 days before first dose of study treatment. Note: Dose of steroids must be stable for 5 days before the baseline brain MRI.

16. Patient is receiving treatment with any enzyme-inducing anticonvulsant ([Appendix 1](#)) that cannot be discontinued at least 1 week before first dose of study treatment, and for the duration of the study. Patients on non enzyme-inducing anticonvulsants are eligible.

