1.1 Study design

This is a single-arm, open-label, multi-center, phase II study to evaluate the efficacy and safety of the ALK inhibitor LDK378 when used as a single agent in patients with ALK-rearranged, stage IIIB or IV NSCLC previously treated with alectinib. A total of approximately 20 patients will be enrolled into the study. Treatment with LDK378 will continue until the patient experiences disease progression as determined by the investigator according to RECIST 1.1, unacceptable toxicity that precludes further treatment, pregnancy, start of a new anticancer therapy, discontinuation of treatment at the discretion of the patient or investigator, lost to follow-up, death, or termination of the study by Sponsor. LDK378 may be continued beyond RECIST-defined progressive disease (PD) as assessed by the investigator if, in the judgment of the investigator, there may be clinical benefit with continued treatment. In these patients, tumor assessments should continue as per the schedule of assessments until treatment with LDK378 is permanently discontinued. Patients who discontinue the study medication in the absence of progression will continue to be followed with tumor assessments until the time of PD as assessed by the investigator.

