The analysis of QT data is complicated by the fact that the QT interval is highly correlated with heart rate. Because of this correlation, formulas are routinely used to obtain a corrected value, denoted QTc , which is independent of heart rate. This QTc interval is intended to represent the QT interval at a standardized heart rate. For this analysis, the Bazett's correction formula defined as $\text{QTcB} = \text{QT}/\text{SquareRoot}(\text{RR})$ and the Fridericia's correction formula defined as $\text{QTcF} = \text{QT}/\text{CubeRoot}(\text{RR})$, where RR (in seconds) = $60/\text{HR}$, will be used for QT correction.

As described previously, ECG summary tables will include only ECG assessments collected during the on-treatment period. Shift tables, change from baseline summaries, and change score generation may use data from pre-treatment period for baseline calculations. The following summaries will be produced for each applicable ECG parameters.

- For each of ECG parameters (HR, and QT, QTcB, QTcF, QRS, PR intervals), descriptive statistics at baseline, at each post-baseline time point and changes from baseline at each post-baseline time point.
- For each of QT/QTc intervals (QT, QTcB, QTcF), shift tables based on notable parameter categories (≤ 450 , $> 450 - \leq 480$, $> 480 - \leq 500$, > 500 ms) at baseline and the worst post-baseline value observed.
- Frequency counts and percentages of patients having notable ECG values according to the following categories:
 - QT/QTcB/QTcF increase from baseline > 30 ms, > 60 ms
 - Newly occurring post-baseline QT/QTcB/QTcF > 450 ms, > 480 ms, > 500 ms
 - HR increase from baseline $> 25\%$ and value > 100 bpm
 - HR decrease from baseline $> 25\%$ and value < 50 bpm
 - PR increase from baseline $> 25\%$ and value > 200 ms
 - Newly occurring post-baseline PR > 200 ms and ≤ 220 ms, > 220 ms
 - QRS increase from baseline $> 25\%$ and value > 110 ms
 - Newly occurring post-baseline QRS > 110 ms and ≤ 120 ms, > 120 ms

Note the denominator to calculate percentages for each category is the number of patients with both a baseline and a post-baseline evaluation. A newly occurring post-baseline ECG notable value is defined as a post-baseline value that meets the criterion post-baseline but did not meet the criterion at baseline.

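### Newly occurring QT, PR and QRS percentages keep patients who already meet the criterion at baseline in the denominator, and the PR and QRS bands can count an improvement as a new abnormality

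*SAP*

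**What the plan says.** SAP 2.8.2, under ECGs, plans counts and percentages of patients with notable ECG values. One rule covers all rows: "the denominator to calculate percentages for each category is the number of patients with both a baseline and a post-baseline evaluation". The next sentence defines a newly occurring value as a "value that meets the criterion post-baseline but did not meet the criterion at baseline".

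The newly occurring rows are:

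- "Newly occurring post-baseline QT/QTcB/QTcF > 450 ms, > 480 ms, > 500 ms"
- "Newly occurring post-baseline PR > 200 ms and ≤ 220 ms, > 220 ms"
- "Newly occurring post-baseline QRS > 110 ms and ≤ 120 ms, > 120 ms"

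The QT rows are all open-ended. PR and QRS each have one closed band and one open-ended row. The same table also has rows for change from baseline.

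The same section plans shift tables from baseline to worst post-baseline value for QT, QTcB and QTcF, cut at 450, 480 and 500 ms. It plans none for PR or QRS. All ECG values are listed with notable ones flagged, and patients with notable values are listed separately.

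In Protocol 5.3, exclusion 11 bars a QTcF above 470 ms, judged by Fridericia's "correction on the screening ECG (as mean of triplicate ECGs". Sections 5.2 and 5.3 set no numerical limit on uncorrected QT, QTcB, PR or QRS. Under Protocol 7.2.2.6.1 the ECG baseline is the pre-dose recording on Cycle 1 Day 1, which is not the screening ECG used for eligibility.

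**The concern.** A newly occurring row is normally read as the chance that a patient without the abnormality acquires it on treatment. Here the numerator leaves out patients who had it at baseline, while the denominator keeps them. The protocol admits such patients: a screening QTcF of 451 to 470 ms is eligible, although the first SAP cut-off is 450 ms. For an open-ended row the distortion can only make emergence look less frequent.

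QT prolongation is an adverse event of special interest (Protocol 8.1.3), and Protocol 6.4.2.8 reports an analysis that suggested concentration-dependent QTc prolongation. These rows will therefore be read.

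The closed bands have a second problem. Not meeting the criterion at baseline includes being above the band as well as below it, so the definition does not separate worsening from improvement.

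**Working it through.** **Plan's own figure.** The documents state no ECG percentage and no baseline ECG counts, so there is nothing to reproduce.

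**Inputs.**

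- M, patients evaluated at baseline and afterwards: at most about 20, since SAP 1.1 says "A total of approximately 20 patients will be enrolled into the study".
- k, those among M already meeting the criterion at baseline: not in the documents; assumed 0 to 6.
- x, newly occurring cases: not in the documents; 4 is used for illustration.

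**Open-ended rows.** The SAP percentage is x/M. The percentage among patients at risk is x/(M − k). Their ratio is (M − k)/M, so the relative shortfall is k/M whatever x is, provided x is at least 1. With M = 20 and x = 4:

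| k (assumed) | SAP figure | At-risk figure | Relative shortfall |
|---|---|---|---|
| 0 | 4/20 = 20.0% | 4/20 = 20.0% | 0% |
| 1 | 20.0% | 4/19 = 21.1% | 5% |
| 2 | 20.0% | 4/18 = 22.2% | 10% |
| 4 | 20.0% | 4/16 = 25.0% | 20% |
| 5 | 20.0% | 4/15 = 26.7% | 25% |
| 6 | 20.0% | 4/14 = 28.6% | 30% |

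If only 18 patients are evaluable, each patient already above costs 1/18 = 5.6% instead of 5%. The number of cases does not change in any of these scenarios.

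**Where k can exceed zero.**

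- QTcF >450 ms: plausible, because 451 to 470 ms may enter.
- QTcF >480 and >500 ms: close to nil, because screening values above 470 ms are excluded. It is not exactly nil, because baseline is a later ECG.
- QTcB: plausible. From the SAP's formulas, QTcB = QTcF × RR^(−1/6). At an assumed heart rate of 90 bpm, RR = 60/90 = 0.667 s and the factor is 1.070. A QTcF of 425 ms then gives a QTcB of about 455 ms, and an eligible QTcF of 460 ms gives about 492 ms.
- Uncorrected QT, PR and QRS: possible, as no entry limit applies.

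**Closed bands.** Take a baseline PR of 230 ms and a later value of 210 ms. The band is >200 to 220 ms. The baseline is outside it and the later value is inside it, so the definition is met and a shortening is counted as a new abnormality. The QRS band of >110 to 120 ms behaves in the same way. This error raises the numerator, so the net direction in the band rows cannot be stated in advance.

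**Change-from-baseline rows.** Every patient with both evaluations can show a change, so the present denominator is reasonable there.

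**The case against.** The strongest reply is that this is a declared convention. The denominator and the definition stand in adjacent sentences, and as a share of all evaluable patients the percentage is correct. It is low only as an estimate of risk among patients free of the abnormality at baseline. That is true and limits the point.

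For QT the reply is stronger. The shift tables use the same cut-offs as the newly occurring rows, and unscheduled ECGs feed both, so the at-risk denominator and the number crossing each threshold can be read off. Adverse events of special interest are summarised separately by preferred term and do not use this denominator. With about 20 patients, counts alongside percentages and full listings, the alternative can be rebuilt by hand. No test or decision rule uses these figures, and 4/20 has an exact 95% interval of about 6% to 44%, far wider than the shifts in the table.

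The reply does not reach PR and QRS, which have no shift table. Nor does it touch the band definition, which is a fault in the count itself.

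A reader might infer that all the newly occurring ECG rates are understated, or that a QT signal would be hidden. The documents do not support either reading. The effect depends on baseline counts that are not given, is close to nil for QTcF >480 and >500 ms, and can be recovered for QT from planned output. In the band rows a patient starting above the band can be counted as new, so the bias there is not one-directional.

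**Conclusion.** The point holds in a limited form. For open-ended newly occurring rows, the SAP percentage equals the at-risk percentage times (M − k)/M. This is a relative loss of 5% per patient already above the cut-off when M = 20, and no loss if k = 0 or there are no new cases. Every k and x used here is assumed. The practical gap is in PR and QRS, where no planned table supplies the at-risk denominator and where the closed bands can record an improvement as a new abnormality. The output is descriptive, the listings are unaffected, and the severity is minor.

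**What to change.** In SAP 2.8.2, ECGs:

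1. For each newly occurring row, take as denominator the patients with both evaluations whose baseline did not meet that row's criterion.
2. For PR >200 to 220 ms and QRS >110 to 120 ms, require a baseline at or below the lower limit (200 ms and 110 ms) in both numerator and denominator.
3. Show n/m beside each percentage.
4. Keep the present denominator for the change-from-baseline rows.

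This takes one or two sentences and no new data. The cost is that denominators differ from row to row, which n/m makes visible.

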4.8.1 Multiple assessments within post-baseline visits

For all analyses regarding abnormal assessments or analyses based on worst or best post-baseline value (e.g., laboratory, ECGs, vital signs, ECOG performance status), all post-baseline values will be included (scheduled, unscheduled, repeat) unless otherwise specified. All unscheduled and repeat measurements will be included in listings.

Laboratory Data

Local laboratories will be used for laboratory evaluations in this study. However, if laboratory assessments are collected from both local and central laboratories on the same date, analyses are as follows. For shift tables using CTC grades to compare baseline to the worst post-baseline value, the assessment with worst post-baseline value is used for analyses irrespective of the source. For LFT summaries, where concurrent measurements are used in the calculation of number and percentage of patients with worst post-baseline values, the assessment with worst post-baseline value is used (since worst values are based on the largest ratio of lab value to its ULN for each patient) although the worst values for the different parameters may be coming from different laboratories.

ECGs

ECG data will be analyzed based on local laboratory reported results. At each scheduled time-pint, the triplicate ECGs will be taken as per protocol and the summary (mean) of their measurements for each ECG parameter will be collected in the [12 Lead ECG Evaluation – Local Analysis] eCRF page. Thus the mean of measurements associated with the scheduled time point will be used for the analyses.

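### The SAP's definition of a newly occurring ECG value counts shortening into the bounded PR and QRS bands as a new notable value (minor; two rows of a descriptive table)

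*SAP*

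**What the plan says.** The ECG part of SAP 2.8.2 plans counts and percentages of patients with notable values. Three rows use the term newly occurring:

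- QT: "Newly occurring post-baseline QT/QTcB/QTcF > 450 ms, > 480 ms, > 500 ms"
- PR: "Newly occurring post-baseline PR > 200 ms and ≤ 220 ms, > 220 ms"
- QRS: "Newly occurring post-baseline QRS > 110 ms and ≤ 120 ms, > 120 ms"

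A note under the list defines the term as "a post-baseline value that meets the criterion post-baseline but did not meet the criterion at baseline". The same note sets the denominator: "the denominator to calculate percentages for each category is the number of patients with both a baseline and a post-baseline evaluation". Patients already above a band at baseline therefore stay in the table.

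SAP 4.8.1 says that for analyses of abnormal, worst or best values, "all post-baseline values will be included (scheduled, unscheduled, repeat) unless otherwise specified". SAP 2.8.2 confirms that unscheduled ECGs enter the analysis of notable changes. Shift tables, which would show direction, are specified only for QT: "For each of QT/QTc intervals (QT, QTcB, QTcF), shift tables based on notable parameter categories". The one ECG-interval limit among the exclusion criteria (protocol 5.3) concerns QTcF, so a baseline PR above 220 ms or QRS above 120 ms is not ruled out by any stated limit.

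**The concern.** The definition suits a one-sided threshold: a patient who exceeds 480 ms after baseline, and did not before, must have risen. It does not suit a band with an upper limit, because a patient can fail the criterion at baseline by being too high. When that patient's interval shortens into the band, the criterion becomes met and the patient is counted as newly notable.

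ECGs are a named safety endpoint (protocol Table 3-1, SAP Table 1-1), and readers will take the row as treatment-emergent prolongation. With about 20 patients, a single such count is visible. The other PR and QRS rows require a rise of more than 25%, and the vital-sign criteria require a directional change or a one-sided limit. Only the two lower band rows lack such a guard.

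**Working it through.** The plan gives no figure to reproduce here, so the check applies the rule as written and then sizes its effect.

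**1. Rule applied literally.** Count a patient if the criterion is met after baseline and was not met at baseline. The last column requires baseline at or below the band's lower limit and the maximum post-baseline value within the band.

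| Baseline → post-baseline (ms) | Counted: any value | Counted: worst value | Counted with the fix |
|---|---|---|---|
| PR 230 → 210 | yes | yes | no |
| PR 230 → 210, 228 | yes | no | no |
| PR 190 → 210 | yes | yes | yes |
| PR 190 → 210, 230 | yes | no | no (upper row only) |
| QRS 130 → 115 | yes | yes | no |
| QRS 100 → 115 | yes | yes | yes |

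**2. Which rows are exposed.** On a grid of whole milliseconds, count the pairs in which the interval decreases yet is flagged as new:

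- PR band, baselines up to 259 ms: 39 baselines (221–259) × 20 band values (201–220) = 780 pairs.
- QRS band, baselines up to 149 ms: 29 baselines (121–149) × 10 band values (111–120) = 290 pairs.
- QT limits 450, 480 and 500 ms: none. A value above a limit cannot be lower than a baseline at or below it. The same reasoning clears PR >220 and QRS >120 ms.

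**3. Size per patient.** 1/20 = 5 percentage points.

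**4. Chance of a false count with no drug effect.** The setting is a patient with baseline above the band and seven post-baseline ECGs (Cycle 1 Day 15 and Day 1 of Cycles 2 to 7, from protocol Table 7-5). Visit values are taken as independent and normal around the patient's true value. The SDs are assumptions; the documents give none. Let p be the probability that one visit falls in the band. Then any-value chance = 1 − (1 − p)^7, and worst-value chance ≈ p^7, since all seven must be at or below the upper limit.

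| True value, SD (ms) | p | Any value | Worst value |
|---|---|---|---|
| PR 225, SD 6 | 0.202 | 79% | 0.001% |
| PR 230, SD 6 | 0.048 | 29% | below 0.001% |
| PR 225, SD 8 | 0.265 | 88% | 0.009% |
| PR 230, SD 8 | 0.105 | 54% | below 0.001% |
| QRS 124, SD 4 | 0.158 | 70% | below 0.001% |

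At a smaller assumed SD of 3.5 ms, the any-value figures are 43% (PR 225) and 1.5% (PR 230). Far above the band they are also small: under 5% for PR 240 ms at SD 6–8, and about 0.1% for QRS 135 ms at SD 4. With a single post-baseline ECG the two readings coincide, and the chance is p: 20% for PR 225 ms at SD 6 and 16% for QRS 124 ms.

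**The case against.** The literal reading of the definition is not in dispute. The case on the other side concerns its weight.

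- **The large percentages depend on one reading.** A reader might infer from SAP 4.8.1 that one visit in the band is enough. That section says which values are eligible, not whether a patient is classified by any value or by the worst. The QT shift tables and the liver-test counts use the worst value. Under that reading, chance fluctuation over seven visits almost never produces a count. This objection stands. What survives it is genuine shortening, with every value at or below the upper limit, which is miscounted under both readings.
- **The SDs are unsupported.** Scheduled values are means of triplicate ECGs, which reduces noise. This stands, and is why the 3.5 ms figures are shown.
- **Few patients may qualify.** Protocol 5.3 excludes significant uncontrolled heart disease and several arrhythmias, and protocol 7.2.2.6.1 requires clinically significant ECG findings to be discussed with the sponsor before enrolment. Neither is a PR or QRS limit, but the number exposed may be zero.
- **A case can be traced.** Change-from-baseline statistics for PR and QRS, a flagged listing of all ECGs and a separate listing of patients with notable values are planned. They would let a reader find the case, but they do not correct the summary count.
- **Adverse events of special interest.** A reader might tie this to QT prolongation or bradycardia, which are on that list. PR and QRS prolongation are not (protocol 8.1.3, SAP 2.8.2), and the QT and heart-rate rows are directional, so the link gives no support.

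**Conclusion.** The point holds as a minor defect. As written, the definition counts shortening into the PR >200 to ≤220 ms or QRS >110 to ≤120 ms band as newly occurring, and nothing else in the SAP overrides it. It affects two rows of a descriptive table and has no bearing on the primary endpoint.

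Each affected patient adds about 5 percentage points at N=20. How many there will be depends on the number with baseline PR >220 or QRS >120 ms, which the documents do not give. The 29–88% range is conditional on such a baseline just above the band, on the assumed SDs (PR 6–8 ms, QRS 4 ms) and on the any-value reading. It should not be read as an expected error rate for the table. Under the worst-value reading the same settings give about 0.01% or less. That the SAP leaves the choice open is itself worth settling.

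**What to change.** Add one sentence to the note in SAP 2.8.2: for the PR >200 to ≤220 ms row, a value is newly occurring only if baseline PR is ≤200 ms and the worst (maximum) on-treatment post-baseline PR lies within the band; for the QRS >110 to ≤120 ms row, the same with baseline QRS ≤110 ms. Keep the present rule for the upper rows (baseline not >220 ms, not >120 ms). The QT rows need no change.

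Both conditions are needed. The baseline condition alone would stop improvements being counted, but would leave open whether any value or the worst value classifies the patient.

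The cost is one sentence and one line of programming, with no new data. There is a small downside: the two PR rows become mutually exclusive, as do the two QRS rows. A patient going from 190 to 215 to 230 ms appears only in the upper PR row, and a table footnote should say so.

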2.8.2 Safety

All safety analyses will be performed based on the Safety Set. All listings and tables will be presented for all patients, unless otherwise specified.

Baseline

Baseline is the result of an investigation describing the “true” uninfluenced state of the patient. The last available assessment before or on the start date of study drug is defined as “baseline” value or “baseline” assessment. If an assessment is planned to be performed prior to the first dose of study drug in the protocol and the assessment is performed on the same day as the first administration of study drug, it will be assumed that it was performed prior to study drug administration, if assessment time or first dose time is not collected or is missing. If assessment time and first dose time are collected, the observed time point will be used to determine pre-dose on study day 1 for baseline calculation. Unscheduled assessments before the start date of study drug will be used in the determination of baseline. See [Section 4.8.2](#) for further details on derivation of baseline for laboratory data and ECGs.

Patients who start study treatment and discontinue from the study on the same day may have 2 different sets of data collected on study day 1, one being reported to the cycle 1 day 1 visit, the other reported to the end of treatment (EOT) visit. Data reported at the EOT visit are not eligible for baseline selection.

Grouping for the analyses

The overall observation period will be divided into three mutually exclusive segments:

- Pre-treatment period: from day of patient’s informed consent to the day before first dose of study drug.
- On-treatment period: from day of first dose of study drug to 30 days after last dose of study drug (Note: for ongoing patients, from day of first dose of study drug to the data cut-off date).
- Post-treatment period: starting at day 31 after last dose of study drug.

The safety summary tables will include only assessments collected during the on-treatment period, i.e., assessments collected no later than 30 days after last dose of study drug and assessments collected before or on the data cut-off date for ongoing patients, unless otherwise specified.

For select items, shift tables or change from baseline summaries generated for laboratory, ECG, vital signs and change score generation may use data from pre-treatment period for baseline calculations.

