Unscheduled ECG measurements will not be used in computing the descriptive statistics for change from baseline at each post-baseline time point. However, they will be used in the shift table analysis of notable QT/QTc intervals and the analysis of notable ECG changes.

All ECG parameters will be listed and the notable values will be flagged in the listing. In addition, patients with notable ECG values will be listed separately.

Vital signs

Vital sign assessments will be performed in order to characterize basic body function. The parameters collected are weight (kg), body temperature ($^{\circ}\text{C}$), pulse rate (beats per minute), systolic and diastolic blood pressure (mmHg).

As described previously, vital sign summary tables will include only vital sign assessments collected during the on-treatment period. Shift tables, change from baseline summaries, and change score generation may use data from pre-treatment period for baseline calculations. The following summaries will be produced for each of vital sign parameters (weight, body temperature, pulse rate, systolic and diastolic blood pressure).

- Descriptive statistics at baseline, at each post-baseline time point and changes from baseline at each post-baseline time point.
- Shift table based on values classified as notable low, normal, notable high, or notable (high and low) at baseline and the worst post-baseline value observed.

Clinically notable elevated values are defined as:

- Systolic BP: ≥ 160 mmHg and an increase ≥ 20 mmHg from baseline
- Diastolic BP: ≥ 100 mmHg and an increase ≥ 15 mmHg from baseline
- Body temperature: $\geq 39.1^{\circ}\text{C}$
- Weight: increase from baseline of $\geq 10\%$
- Pulse rate: ≥ 120 bpm with increase from baseline of ≥ 15 bpm

Clinically notable below normal values are defined as:

- Systolic BP: ≤ 90 mmHg and a decrease ≥ 20 mmHg from baseline
- Diastolic BP: ≤ 50 mmHg and a decrease ≥ 15 mmHg from baseline
- Body temperature: $\leq 35^{\circ}\text{C}$
- Weight: decrease from baseline of $\geq 10\%$
- Pulse rate: ≤ 50 bpm with decrease from baseline of ≥ 15 bpm

All vital sign parameters (including height and BMI at screening) will be listed and the notable values will be flagged in the listing. In addition, patients with notable vital sign values will be listed separately.

ECOG (WHO) performance status

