4.8.2 Baseline

As defined in [Section 2.8.2](#), the last available assessment before or on the start date of study drug is defined as ‘baseline’ value or ‘baseline’ assessment.

Laboratory data

Local laboratories will be used for laboratory evaluations in this study. However, if both local and central laboratory assessments are performed on the same date and corresponding to the baseline assessment date, then the central laboratory assessment will be used for the calculation of baseline.

ECGs

Baseline for ECG measurement is the mean of the pre-dose replicate measurements on the baseline day. For the calculation of the mean, unscheduled assessments will not be combined with scheduled assessments. The mean will be calculated separately for scheduled and unscheduled. Note in this study the mean of replicate measurements at each time point is collected on the [12 Lead ECG Evaluation – Local Analysis] eCRF page and thus individual measurements are not entered in the database.

Study day 1 scheduled pre-dose ECGs will be considered to have been obtained prior to study drug administration. If a scheduled pre-dose measurement actually occurred post-dose, then the corresponding measurement will be treated and analyzed similar to an unscheduled post-dose measurement. Unscheduled assessments on study day 1 will be considered as post-baseline.

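### In the SAP's safety tables, four of five vital signs can never be notable at baseline, and an unscheduled Day 1 ECG known to precede the first dose counts as post-baseline

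*SAP*

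**What the plan says.** **Vital signs.** SAP 2.8.2 (Vital signs) plans, for weight, temperature, pulse, systolic and diastolic pressure, a "Shift table based on values classified as notable low, normal, notable high, or notable (high and low) at baseline" and at the worst post-baseline value. It then gives one set of rules, introduced by "Clinically notable elevated values are defined as" and followed by a matching list for low values. The blood-pressure rules join a limit to a change ("mmHg and an increase", "mmHg and a decrease"). Pulse is built the same way. Weight is defined by a 10% change alone, and temperature by limits alone. No separate rule is given for classifying the baseline value.

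**ECGs.** SAP 2.8.2 (Baseline) says that, where times are collected, "the observed time point will be used to determine pre-dose on study day 1 for baseline calculation", and it refers to SAP 4.8.2 for ECG detail. SAP 4.8.2 then states: "Unscheduled assessments on study day 1 will be considered as post-baseline". On where unscheduled ECGs are used, SAP 2.8.2 (ECGs) says "they will be used in the shift table analysis of notable QT/QTc intervals and the analysis of notable ECG changes". Protocol 7.2.2.6.1 defines ECG baseline as the Cycle 1 Day 1 assessment made before dosing, and lets the investigator repeat an ECG whenever wanted.

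**The concern.** A shift table is read by comparing a patient's class before and after treatment. If the baseline class is normal by construction, a pre-existing abnormality is hidden, and the table cannot separate patients who started outside the limits from those who started within them. This matters most for pulse, because bradycardia is an adverse event of special interest (Protocol 8.1.3; SAP 2.8.2).

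The ECG rule works in the opposite direction. A value obtained before any drug was taken can appear in the on-treatment QT tables as a worst post-baseline value or a newly occurring notable value. QT prolongation is also an adverse event of special interest, and in a trial of about 20 patients one misplaced value is visible in a percentage.

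**Working it through.** The plan gives no figure on either point, so there is none to reproduce. The check applies the rules as written.

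**1. Vital-sign classes at baseline.** Inputs are the SAP 2.8.2 definitions:

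| Parameter | Notable high | Notable low |
|---|---|---|
| Systolic (mmHg) | ≥160 and rise ≥20 | ≤90 and fall ≥20 |
| Diastolic (mmHg) | ≥100 and rise ≥15 | ≤50 and fall ≥15 |
| Pulse (bpm) | ≥120 and rise ≥15 | ≤50 and fall ≥15 |
| Weight | rise ≥10% | fall ≥10% |
| Temperature (°C) | ≥39.1 | ≤35 |

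At baseline, change = baseline − baseline = 0, so no condition on a rise or fall can be met. The number of baseline values classed as notable over wide ranges was:

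- systolic 60–240 mmHg: 0 of 181
- diastolic 30–150 mmHg: 0 of 121
- pulse 30–200 bpm: 0 of 171
- weight 30–150 kg: 0 of 121
- temperature 34.0–42.0 °C in steps of 0.1: 41 of 81

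A baseline systolic pressure of 88 mmHg or a pulse of 48 bpm is therefore classed as normal.

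**2. What the table then shows.** Take a pulse of 48 at baseline and 40 at worst. The baseline class is normal. The post-baseline value meets the limit of 50, but the fall is 48 − 40 = 8, under 15, so it is also normal. The table reads normal to normal.

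**3. Choice of remedy.** Take systolic 165 rising to 175, a rise of 10.

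- Rules as written: normal to normal.
- Limits alone at baseline, two-part rule afterwards: notable high to normal, a false improvement.
- Limits alone at both time points: notable high to notable high.

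Only the last describes the patient correctly. Weight has no absolute limit, so it has no baseline class under any of these.

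**4. Path of an unscheduled pre-dose Day 1 ECG.** The on-treatment period begins on the day of first dose (SAP 2.8.2). Worst-value analyses include unscheduled and repeat values (SAP 4.8.1). Unscheduled ECGs enter the notable QT/QTc shift table and the notable-change analysis (SAP 2.8.2). Scheduled and unscheduled values are not averaged together (SAP 4.8.2), so the scheduled pre-dose mean remains the baseline.

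Assumed case: scheduled pre-dose QTcF 440 ms, unscheduled pre-dose repeat 485 ms.

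- Increase: 485 − 440 = 45 ms, which exceeds 30 but not 60.
- Newly occurring above 450 ms: yes (440 did not meet it).
- Newly occurring above 480 ms: yes. Above 500 ms: no.

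All of this is scored before any dose. One patient of 20 evaluable is 1/20 = 5 percentage points.

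**5. When an event is actually added.** Either the baseline value did not already meet the criterion, or the increase exceeds 30 or 60 ms for the change categories. In addition, no later on-treatment value may meet the same criterion, since the patient would then be counted anyway.

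**The case against.** **Vital signs.** Exclusion criterion 11 bars systolic pressure of 160 or more and/or diastolic of 100 or more, the same limits as the SAP's notable-high classes. A high-pressure baseline would need a rise between screening and Day 1 or an eligibility deviation. That stands, and it moves the practical effect to low pressure and to pulse, for which criterion 11 sets no numerical limit. A reader might infer that abnormal baselines are lost from the report altogether. They are not: temperature is classified properly, baseline and change statistics are tabulated, and all vital signs are listed. It could also be said that a programmer would simply apply the limits at baseline. The SAP does not say so, and weight has no limit to apply.

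**ECGs.** A reader might see a flat contradiction between SAP 2.8.2 and 4.8.2. The text does not go that far. The timing sentence in 2.8.2 concerns assessments planned before the first dose, unscheduled assessments are admitted to baseline only when they fall before the start date, and 2.8.2 hands ECG detail to 4.8.2. The rule can fairly be read as a deliberate convention that errs towards counting QT events. Even so, it labels a value known to be pre-dose as post-baseline, which does not fit the protocol's pre-dose baseline. SAP 4.8.2 itself uses actual timing to move a scheduled ECG that turned out to be post-dose, with no mirror rule for an unscheduled ECG that was pre-dose.

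A reader might also infer that every pre-dose repeat above a threshold adds a false event. The newly-occurring definition in SAP 2.8.2 rules that out: if a repeat was prompted by a long scheduled QTcF, the baseline may already meet the criterion.

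**Conclusion.** Both points hold as minor defects in descriptive safety tables. The primary endpoint, the sample size and its operating characteristics are untouched.

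For vital signs, four of the five parameters have an empty notable class at baseline whatever the data. This follows from the definitions and needs no assumption. The practical consequence is mainly for low blood pressure and for low or high pulse.

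For ECGs, the consequence is conditional. It needs an unscheduled Day 1 ECG before the first dose that meets the conditions in step 5 of the working. Each such patient is 5 percentage points if 20 are evaluable, but the documents give no basis for saying how many there would be. The 440 and 485 ms values are illustrative.

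**What to change.** **SAP 2.8.2, Vital signs.** In the shift table, classify systolic pressure, diastolic pressure, pulse and temperature by the absolute limits alone at both baseline and worst post-baseline. Remove weight from the shift table and report the number of patients with a post-baseline increase or decrease of 10% or more. Keep the two-part rule for flagging and listing notable post-baseline values.

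**SAP 4.8.2, ECGs.** Where the ECG time and the first-dose time are both recorded, treat an unscheduled Day 1 ECG taken before the first dose as pre-treatment and exclude it from post-baseline analyses. Keep the post-baseline default when either time is missing. State also that the scheduled pre-dose mean remains the baseline, so that the change does not alter baseline selection.

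**Cost.** SAP wording and minor programming before database lock. The documents do not show whether times are collected for unscheduled ECGs. The ECG rule is therefore conditional on recorded times and asks for no new data; if times are absent, the present default continues to apply.
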